Ketamine, a phencyclidine derivative, has been in clinical use since 1958. It exerts its analgesic, amnestic and anesthetic effects on the brain and spinal cord by inhibiting presynaptic release of glutamate, an excitatory neurotransmitter, and non-competitively blocking calcium influx via NMDA receptor channels. Ketamine is also thought to activate mu and kappa opioid receptors (not reversible by naloxone) as well as blocking voltage-gated sodium channels like local anesthetics. Furthermore, ketamine has anticholinergic properties that promote bronchodilation (beneficial for asthmatics) and

tachycardia, which can be useful for hemodynamically unstable patients. The thalamo-neocortical and limbic systems are dissociated with ketamine i.e., the patient appears awake, with preserved pharyngeal and laryngeal reflexes, but is unresponsive and catatonic. Unlike narcotics, ketamine has the advantage of immediate, profound analgesia without life-threatening respiratory depression. Ketamine 125 – 250 µg/kg IV produces analgesia within 1-2 minutes, and has a duration of approximately five minutes (24).

Side effects (pupillary dilatation, nystagmus, dizziness, salivation, lacrimation, hallucinations) are dose-dependent and extremely rare in the analgesic dose range for ketamine. Doses to achieve analgesia with ketamine are much lower than that for anesthetic induction (2 to 10 mcg/kg/min IV vs. 1-3 mg/kg IV one time). In fact, most side effects are primarily reported with ketamine induction doses (19, 20). Even so, the drug was well tolerated and hallucination events were no different from placebo in a randomized, double-blind trial of intraoperative ketamine for spine surgery (7). Hallucinations and ketamine-induced cardiovascular stimulatory effects can be prevented by premedicating the patient with low-dose benzodiazepines (19, 20). Thus, with standard analgesic dosing and preemptive medications, ketamine side effects are virtually negligible.

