2. Methadone group: Will receive a single dose of IV methadone (0.2 mg/kg) preinduction.
3. Ketamine + methadone group: Will receive methadone (0.2 mg/kg) preinduction, a bolus of IV ketamine (0.5 mg/kg) during induction and and IV ketamine infusion intraoperatively (5 mcg/kg/min)

Perioperative anesthetic management will be standardized as well as post-anesthesia care unit (PACU) IV opioid administration, which will be based on verbal-rating scale (VRS) pain scores. Patients will be discharged from the PACU and sent to the floor. They will be placed on a pain medication regimen that often includes oral and IV narcotics as needed (PRN). Opiate consumption, VRS pain scores, and adverse events will be recorded on post-operative days one to three and at six weeks.

METHODS

I. Recruitment

- a. Study investigators will contact surgeons who routinely perform lumbar spine surgery and present the study protocol to the surgeons. During the preoperative visit (3 to 15 days prior to surgery), the surgeons and/or assistants will hand the study material packet to potential subjects. Those interested in participating will sign the initial patient contact letter, which includes their phone number and e-mail address.
- b. Study investigators will call these patients, explain the study protocol including the potential risks, benefits, and alternatives and address any questions/concerns. In this manner, potential subjects will have more than 24 hours to decide on signing the consent document.
- c. Only patients providing written consent and indicated that they have been introduced to the study prior to meeting with the anesthesiologists on the day of surgery will be able to participate and undergo screening.
- d. Screening procedures (see inclusion and exclusion criteria section) will ensure subjects meet all inclusion criteria. They will be subsequently randomized to one of three study groups according to a computer-generated randomization number table.

II. Study Medication Administration Protocol

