administration i.e., syringe #1 will be given pre-induction, syringe #2 will be given during induction, and syringe #3 will be infused over the duration of the surgery. To prevent accidental administration of 3 placebos, all syringes will have an additional random 4 letter label: those containing any vowel (A, E, I, O, U) at the end of the 4 letter combination will be designated as placebo syringes. The unblinded investigator will double check that no more than 2 syringes have this letter combination prior to handing off the syringes to the anesthesiologist. Once this has been verified, he will place a sticker over the alphabetic code to further blind the recruiter in case the placebo blinding procedure has been discovered. In the extremely rare event that the patient accidentally receives 3 placebos (no study drug), there is a rescue medication algorithm that calls for administering IV fentanyl boluses or increasing anesthetic depth to control pain. Date, IRB number, and subject number will be the only other labeling allowed on these syringes. Only the aforementioned unblinded M.D. investigators will know the syringe identities. However, the anesthesiologist can always be unblinded for emergencies that require identification of the study drug to direct appropriate treatment e.g., undocumented allergic reaction to the study medication, unexplained hemodynamic instability, unexplained altered mental status, etc. The unblinded investigator will meet with the anesthesiologist after the case is finished to report the amount of study drug given for pharmacy and billing purposes. The data collector, recruiter, surgeon, and nurses involved with the subject's care will not be allowed to review the anesthetic record unless given permission by the P.I. Only after the subject's completion of the study shall they have access.

Group	Study Medication (note - dose based on ideal body weight (IBW) in kg)
Ketamine	Preinduction: Sham methadone (0.9% normal saline IV bolus, volume (mL) equal to calculated methadone dose of 0.2 mg/kg) Induction: ketamine 0.5 mg/kg IV bolus Infusion: ketamine 5 mcg/kg/min IV
Methadone	Preinduction: 0.2 mg/kg methadone IV bolus Induction: Sham ketamine (0.9% normal saline IV bolus, volume (mL) equal to calculated ketamine induction dose of 0.5 mg/kg) Infusion: Sham ketamine (0.9% normal saline IV, rate equal ketamine infusion rate of 5 mcg/kg/min)

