Test significance level, α	0.050	0.025	0.050	0.025
1 or 2 sided test?	2	2	2	2
Group 1 mean, μ_1				
Group 2 mean, μ_2				
Difference in means, $\mu_1 - \mu_2$	2.000	2.000	1.800	1.800
Common standard deviation, σ	2.000	2.000	2.000	2.000
Effect size, $\delta = \mu_1 - \mu_2 / \sigma$	1.000	1.000	0.900	0.900
Power (%)	80	80	80	80
n per group	17	21	21	25

Based on the power analysis, a sample size of 38 patients for each group will sufficiently allow us to detect at least a 30% reduction in postoperative opioid consumption and VAS pain scores with 80% power using a two sample t-test, significance level of 0.05 (two-sided). Total sample size will be 114.

ANOVA will be used to compare the continuous variables among the three treatment groups, and when significant differences are determined, a Newman-Keuls multiple-comparison test will be used to determine intergroup differences. Continuous data not normally distributed are analyzed by Kruskal-Wallis test, and when a significant difference is found, a Mann-Whitney U test is used for post-hoc comparisons between the intergroups. Chi-squared test (or Fisher's exact test) is used to analyze the categorical variables such as side effects and sex distribution.

INCLUSION & EXCLUSION CRITERIA

I. Inclusion criteria:

- 18 – 80 years old of either gender, scheduled for elective lumbar laminectomy

II. Exclusion criteria:

- ASA IV and above
- Intolerance, allergy, or contraindication to use of any medications used in this study
- Significant coronary artery disease (abnormal stress test, myocardial infarction within the last 3 months)
- Increased intraocular pressure (e.g., untreated glaucoma)
- Uncontrolled hypertension (BP > 140/90)
- Sleep apnea AND currently on continuous positive airway pressure (CPAP)
- Increased intracranial pressure or clinical signs thereof
- History of intracranial surgery, stroke, or brain aneurysm
- Cardiac arrhythmias particularly prolonged QT syndrome
- Drugs known to cause prolonged QT: class IA antiarrhythmics (quinidine, procainamide, dysopyramide), class III antiarrhythmics (sotalol, dofetilide, ibutilide, amiodarone), haloperidol, thioridazine, arsenic trioxide, HIV protease inhibitors, tricyclic antidepressants
- Individuals with significant psychological disorders including: schizophrenia, mania, bipolar disorder or psychosis
- Pregnant or lactating women
- Emergent laminectomy
- Those already receiving ketamine or methadone prior to surgery

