- Morbid obesity (BMI > 40 kg/m²) AND/OR weight \geq 150 kg
- Chronic renal failure (creatinine > 2.0 mg/dL)
- Liver failure e.g., active cirrhosis
- Alcohol or substance abuse within in the past 3 months
- Uncorrected hypokalemia, hypomagnesemia, hypocalcemia (can be due to diuretics, mineralocorticoid use, laxatives)
- COPD/Hypercarbia
- Restrictive lung disease (pulmonary fibrosis, myasthenia gravis)
- Congestive heart failure
- Thyroid disease
- Organ transplant patients
- Drugs/substances known to inhibit methadone metabolism: macrolide antibiotics e.g., erythromycin, cimetidine, astemizole, voriconazole, grapefruit juice

DATA HANDLING/RESOURCING

Investigators will have access to the patients' medical records and the results of all examinations undertaken as part of this clinical trial. All data will be recorded in forms provided by the investigators. Collected data will be coded and used for research purposes only.

SUBJECT RECRUITMENT

Study investigators will contact surgeons and present this study protocol to them. Prior to surgery, (ideally during patients preoperative appointments) the surgeon will inform the patient of this study and obtain a consent for contact letter signed by the interested patient. The patient will also be provided with an informed consent form. Study staff will follow-up with the surgeon's office (or vice-versa) and conduct a phone interview with the patient to determine eligibility. Patients who intend on participating in the study will sign the informed consent form and the investigator will record that the subject has had completed their informed consent well before the scheduled procedure. Risk and benefits will be reviewed with the subject. They reserve the right to voluntarily exit the study at any time without any penalty. Patients will be explained that general anesthesia will be used during the study.

POTENTIAL RISKS

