Ketamine has been approved by the FDA and is used widely in the U.S. for anesthetic and pain management arenas. It has been well-studied in both animal model and human subjects. Of note, the side effect likelihood listed below for ketamine represent the induction dose side effect profile. Ketamine side effects are dose-dependent, and subanesthetic ketamine doses such as that used for analgesia are mild and less likely to occur (6). For instance, CNS side effects (dizziness, dysphoria, confusion, drowsiness, hallucinations) analyzed from pooled data did not reveal any significant differences: 18% in postoperative ketamine plus morphine vs. 15% in morphine PCA groups ($P = 0.31$; RR, 1.27; 95% CI, 0.80, 2.01) (23). Incidence of CNS side effects for ketamine patients were 18%, 10%, 9%, and 0.7% with IV PCA, IV infusion, IV single dose, and epidural groups. The psychogenic effects (dysphoria, confusion, hallucinations) will be mitigated by midazolam premedication. Patients with significant coronary artery disease (abnormal stress test, recent angina, MI within the last 3 months) will be excluded due to increased cardiac demand (from increased blood pressure, tachycardia). Patients with increased intracranial pressure (ICP) and untreated high intraocular pressure (IOP) will also be excluded from the study.

	Very Likely (>25%)	Likely (10-25%)	Less Likely (1-9%)	Rare (<1%)
Ketamine	
 • Blurred vision • Confusion 	
 • Increased or decreased blood pressure or heart rate • Mental or mood instability • Psychotic thoughts • Hallucinations 	
 • Vomiting • Nausea • Nightmares • Drowsiness 	
 • Difficulty talking • Irregular heart rhythms • Muscle tightness • Redness, or swelling at the injection site • Allergic reactions (rash, itching, difficulty breathing)
Methadone	
 • Drowsiness • Dizziness 	
 • Low Blood Pressure 	
 • Slower or faster heart 	
 • Increased intracranial

		
 • Constipation • Nausea • Slowed respiratory rate 	
 • Confusion • Orthostatic hypotension • Dry mouth • Biliary tract spasm • Blurred vision • Stomach cramps • Anxiety 	
 • rate 	
 • pressure

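### The risk section promises to exclude patients with recent angina, but the exclusion list used for screening does not name it

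*Combined protocol and SAP*

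**What the plan says.** The document describes the coronary exclusion twice.

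- **INCLUSION & EXCLUSION CRITERIA, II. Exclusion criteria:** "Significant coronary artery disease (abnormal stress test, myocardial infarction within the last 3 months". The bracket closes there, with two conditions named.
- **POTENTIAL RISKS:** "Patients with significant coronary artery disease (abnormal stress test, recent angina, MI within the last 3 months) will be excluded due to increased cardiac demand". Three conditions are named, and the reason given is ketamine's effect on blood pressure and heart rate.

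Angina is mentioned nowhere else in the document. METHODS, I. Recruitment, item d, tells screeners which text to use: "Screening procedures (see inclusion and exclusion criteria section) will ensure subjects meet all inclusion criteria". SUBJECT RECRUITMENT has study staff "conduct a phone interview with the patient to determine eligibility".

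Two other exclusions could bear on such a patient: "Intolerance, allergy, or contraindication to use of any medications used in this study" and "ASA IV and above". Neither mentions angina.

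**The concern.** The two statements share a heading and two of their items, and differ on the third. The shorter one is the one that screeners are sent to. Recent angina is largely a matter of symptoms, so it tends to come to light when someone asks. A list that leaves it out neither prompts the question in a phone interview nor tells the interviewer what to do with a positive answer.

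At stake is whether a patient whom the protocol says will be excluded can be randomized and given a ketamine bolus and infusion, which the risk section itself links to raised blood pressure, tachycardia and cardiac demand. There is also a consistency problem: two screeners could reach different decisions on the same patient.

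**Working it through.** The plan states no figure on this point, so the check is a comparison of texts followed by simple allocation arithmetic.

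**1. The two lists side by side**

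| Condition | Exclusion criteria | POTENTIAL RISKS |
|---|---|---|
| Abnormal stress test | named | named |
| Infarction within 3 months | named | named |
| Recent angina | not named | named, with no time window |

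**2. Does another criterion catch the patient?** Take a patient with recent angina, no abnormal stress test on record and no infarction within 3 months.

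- *Stress test:* this excludes only someone who has had one. PATIENT DATA COLLECTION, II, lists a 12-lead EKG among the preoperative data but no stress test.
- *ASA class:* classes I to III are eligible (METHODS, III, item b), and the documents do not tie angina to class IV.
- *Contraindication line:* angina is not listed as a contraindication to ketamine, so applying this line takes clinical judgement.
- *The parent term, significant coronary artery disease:* this applies if the bracket is only illustrative. Other lines in the same list mark their examples with e.g.; this one does not.

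No criterion excludes the patient by name. Each route to exclusion depends on interpretation.

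**3. Chance of receiving ketamine once enrolled.** Inputs: 38 patients per arm, 114 in total, two of the three arms containing ketamine (METHODS, III, item b).

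- One patient: (38 + 38)/114 = 76/114 = 0.667.
- For k such patients enrolled, P(at least one receives ketamine) = 1 − P(all k fall in the methadone-only arm), and the expected number receiving ketamine is 2k/3.

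| k (assumed) | Calculation | P(at least one) | Expected number |
|---|---|---|---|
| 1 | 1 − 38/114 | 0.667 | 0.67 |
| 2 | 1 − (38×37)/(114×113) = 1 − 1406/12882 | 0.891 | 1.33 |
| 3 | 1 − (38×37×36)/(114×113×112) = 1 − 50616/1442784 | 0.965 | 2.00 |

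The values of k are assumptions, since the documents give no angina prevalence. The table does not estimate the chance that such a patient passes screening.

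**4. What protects the patient after enrolment.** BACKGROUND & SIGNIFICANCE states: "Hallucinations and ketamine-induced cardiovascular stimulatory effects can be prevented by premedicating the patient with low-dose benzodiazepines". Midazolam is given to all patients (METHODS, IV, item a), yet POTENTIAL RISKS still calls for exclusion on coronary grounds. In the rescue algorithm (METHODS, V), the cells for hypertension, and for tachycardia with normal pressure, use desflurane, labetalol, hydralazine or fentanyl. None of them reduces the study infusion. METHODS, IV, item f, bars the anesthesiologist from altering the study pump. METHODS, II, provides that "the anesthesiologist can always be unblinded for emergencies that require identification of the study drug", but that comes after exposure.

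**The case against.** The strongest reply is that the document already answers the question. The exclusion is for significant coronary artery disease, and the risk section, using the same heading, gives recent angina as an instance. The bracket may be illustrative: the exclusion list gives two examples of restrictive lung disease, while the risk section speaks of any such disease. That reading is reasonable, but it requires the screener to consult a section to which the protocol does not send them. The missing e.g. leaves the narrower reading open.

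A second reply is that the risk section may simply be loosely worded. It refers to sleep apnea where the list requires sleep apnea with current CPAP, and to liver disease where the list says liver failure. So the documents do not prove that angina was meant to be a criterion. This stands as a caution. Even so, the risk section gives a specific reason for the coronary exclusion, and resolving the conflict towards exclusion is the safer course.

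Third, screening is more than a phone call. Investigators also call patients and have access to medical records. A detailed history, a physical examination, an EKG and a medication list that includes beta-blockers are also collected. No interview script is in the documents, so angina may be asked about. These are real opportunities to find the condition, but the written rule for acting on the finding is still silent.

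Fourth, ketamine is routine at this institution, so the patient might receive it outside the trial. That limits any claim of added risk. It does not remove the contradiction, and in the trial randomization assigns the drug and the treating anesthesiologist is blinded to it.

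Finally, the allocation percentages add little, because two thirds applies to every enrolled patient. That is fair. They show only that an enrolled patient is more likely than not to be exposed.

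**Conclusion.** The concern holds. Two current statements of one safety exclusion disagree, and the one that governs screening omits recent angina. Following the list as written can admit a patient whom the risk section says will be excluded.

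The consequence is limited. Judgement at several steps may well keep such a patient out, and the number affected is probably small. If one is enrolled, the chance of ketamine is 66.7%. With one, two or three enrolled, the chance that at least one receives it is 67%, 89% or 96%, and those counts are assumed. The documents support no estimate of cardiac events. Sample size, endpoints and analysis are not affected. The correction should be made, because it concerns a safety rule and costs almost nothing.

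**What to change.** Add recent angina to the coronary line of the exclusion criteria so that it matches POTENTIAL RISKS. The investigators should choose a look-back window and state it in both places, since neither section now says what recent means. Add a question on angina to the eligibility phone interview.

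The cost is one phrase, one interview question and possibly a few otherwise eligible patients, who are patients the risk section already says should not be enrolled.

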--	--	-----------------------------------------------------------------------------------------------------------------------	-----------------------------------------------------------------------------------------------------------------------------------------------------------------------------------------------------------------------------	----------------------------------------------------------	--------------------------------------------------------------

Methadone carries the same side effect profile as other opiates (constipation, mild drowsiness, pruritus, nausea and vomiting, miosis, respiratory depression), with two chief exceptions - prolonged qTc interval and long-half life. Previous studies suggest that doses as low as 30 mg/day can prolong qTc interval > 0.5 seconds and those who developed Torsades de Pointes (TdP) had doses as low as 40 mg/day (25). 3.6% of subjects receiving methadone developed (TdP) and had abnormal baseline EKG. Erhet et al. also determined that low serum potassium levels, lower serum prothrombin levels (indicative of poor liver function and thus, drug metabolism), and concomitant use of drugs with higher CYP3A4 inhibition were positively associated with prolonged qTc. For our study, we are excluding patients who are morbidly obese, with liver disease, on medications known to inhibit CYP3A4 and/or have arrhythmias in their preoperative EKG.

Since methadone has a half-life of approximately 24-36 hours (22), respiratory depression risk may be increased when additional sedatives are given. Thus, we are excluding any high-risk patients who have poor respiratory status (COPD, any restrictive lung disease, sleep apnea). Nursing will be advised to avoid oversedation. If the patient goes into respiratory depression i.e., respiratory rate < 8 breaths per minute, naloxone (0.1-0.2 mg every 2-3 minutes to keep respiratory rate > 8) can be administered. Supplemental oxygen will be provided to maintain oxygen saturation > 95% during these episodes.

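### The risk section says patients with liver disease are excluded because of the qTc risk, but the hepatic criterion covers only liver failure, so impaired function short of failure passes it

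*Combined protocol and SAP*

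**What the plan says.** Under POTENTIAL RISKS, the paragraph on methadone and qTc reports factors positively associated with prolongation in a cited study. One of them is "lower serum prothrombin levels (indicative of poor liver function and thus, drug metabolism" (the parenthesis closes there). The protocol's answer follows at once: "we are excluding patients who are morbidly obese, with liver disease, on medications known to inhibit CYP3A4 and/or have arrhythmias in their preoperative EKG".

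Eligibility is decided elsewhere. METHODS, I. Recruitment states: "Screening procedures (see inclusion and exclusion criteria section) will ensure subjects meet all inclusion criteria". In that section, under II. Exclusion criteria, the one entry that names the liver reads "Liver failure e.g., active cirrhosis". It carries no laboratory limit and no severity grade.

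BACKGROUND & SIGNIFICANCE describes methadone as metabolized in the liver through CYP3A4 and CYP2D6, and calls QT prolongation its most dangerous potential effect.

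**The concern.** The risk section identifies a hazard (reduced hepatic clearance of methadone, hence a longer qTc) and offers an exclusion as the protection. The exclusion it describes is wider than the one staff will apply. Liver failure is the far end of liver disease, and poor liver function begins well before it. Someone judging the risk section, such as an ethics board member, would believe that a group has been kept out which the list lets in.

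What is at stake is patient safety and the accuracy of the safety case. Staff who follow the list to the letter could give methadone to a patient whom the protocol's own argument treats as excluded. Two of the three arms receive methadone.

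**Working it through.** No arithmetic decides this point. The check is to set the two texts side by side and then ask whether anything else in the protocol closes the gap.

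**1. The qTc exclusions against the list.**

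| Risk section | Exclusion list | Comment |
|---|---|---|
| Morbid obesity | "Morbid obesity (BMI > 40" and so on, with a weight limit | Matches |
| Arrhythmia on the preoperative EKG | "Cardiac arrhythmias particularly prolonged QT syndrome" | Matches |
| CYP3A4 inhibitors | "Drugs/substances known to inhibit methadone metabolism", then a short list | Matches if the heading governs; less clear if only the listed agents count |
| Liver disease | "Liver failure e.g., active cirrhosis" | Narrower |

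Because the third row depends on how the heading is read, I do not use a tally of matches as a measure of size.

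**2. Can the hepatic line be stretched?** The abbreviation e.g. opens the examples, but only examples of liver failure. Even if active cirrhosis is taken to include compensated cirrhosis, non-cirrhotic disease with reduced function still falls outside.

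**3. Does another criterion catch these patients?** The list has 25 entries, and one names the liver. The candidates are:
- ASA IV and above, recent abuse of alcohol or drugs, and organ transplant. Each may remove some patients with hepatic impairment, but none addresses liver function as such.
- "Intolerance, allergy, or contraindication to use of any medications used in this study". This could be applied to a patient with hepatic impairment, but it does not mention the liver and leaves the decision to individual judgment.

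**4. Would laboratory results exclude them?** PATIENT DATA COLLECTION, II. Preoperative data, records abnormal results. No liver test is named, and no hepatic result leads to exclusion. By contrast, the renal criterion in the same list does have a limit (creatinine above 2.0 mg/dL).

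**5. How large is the exposure?** One dose at 0.2 mg/kg of ideal body weight; at 70 kg, 0.2 × 70 = 14 mg IV, which BACKGROUND & SIGNIFICANCE equates to 14 to 28 mg by mouth. That section places the reported QT relationship at 50 to 150 mg IV daily or more. The risk section gives a lower figure, 30 mg/day, without stating the route. Both describe daily dosing, so neither compares directly with a single dose. The trial dose lies below both, but the margin against the second figure is much smaller.

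**6. What other protection is there?** A medical history and physical exam; a preoperative 12-lead EKG; exclusions for arrhythmia and prolonged QT, QT-prolonging drugs, uncorrected electrolyte disturbance and inhibitors of methadone metabolism; and telemetry if the postoperative EKG shows a prolonged qTc. These act on QT risk directly. A baseline EKG does not show how a patient will clear methadone, and the postoperative data list does not name an EKG. The safeguards therefore reduce the consequence of the gap without closing it.

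**The case against.** The best reply is that the risk section is narrative shorthand. Its next paragraph shortens the sleep apnea criterion in the same way: the list requires sleep apnea together with current CPAP use, and the narrative drops the CPAP condition. On that reading, liver disease is only a loose name for the listed criterion, and the authors may have meant failure broadly. The looseness is real, and it means the liver cannot be presented as a lone exception. But a second loose wording is a second mismatch and does not repair the first. The liver sentence directly follows a statement about poor liver function, so its breadth matters to the argument it supports.

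A second reply is that the practical risk is small, given a single dose, a physician's examination and several direct QT controls. That stands, and it sets the grade of this point.

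A third is that the two texts could be aligned the other way, by narrowing the risk section to liver failure. That would remove the inconsistency. It would also leave the stated hazard of poor liver function without a matching exclusion, so widening the criterion is preferable.

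A reader might infer that every liver diagnosis ought to be excluded because the narrative says liver disease. The documents do not support that. The hazard they name is impaired function and metabolism, and a liver diagnosis with preserved function does not raise it.

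**Conclusion.** The inconsistency holds and is minor. The risk section relies on an exclusion of liver disease to answer a qTc hazard from poor liver function, while the operative criterion stops at liver failure. A patient with impaired function short of failure passes that criterion and could be assigned methadone.

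The conclusion assumes that screeners apply the list as written and that no unstated hepatic rule operates locally. How many patients fall in the gap cannot be derived, because the protocol gives no prevalence or liver-test data.

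Two stronger readings should be resisted. A reader might infer that these patients face a likely arrhythmia; with a single dose and the remaining QT safeguards, the protocol does not show that. A reader might also infer damage to the trial's results; no endpoint, comparison or sample-size input depends on this criterion.

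**What to change.** Replace the hepatic criterion with: *Known liver disease with impaired liver function (e.g., abnormal prothrombin time/INR on available preoperative labs, above a limit set by the investigators), including liver failure or active cirrhosis.* Use the same words in the qTc paragraph of POTENTIAL RISKS, so that the safety argument and the eligibility rule describe one population. The limit matters: without it, the word impaired would be left to individual judgment, as the contraindication criterion already is.

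The change is one criterion line and a matching phrase. It costs a small loss of eligible patients. No new test is required, since it relies on known disease and labs already available; a patient with unrecognized impairment and no such labs would still pass. The sleep apnea wording can be aligned in the same edit.
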